1.2 Study design

This will be an open-label, single-arm, multicenter, Phase IIIb study to determine the safety of durvalumab + etoposide and cisplatin or carboplatin as first-line treatment in patients with extensive stage small-cell lung cancer. Patients who fulfil all the inclusion criteria and none of the exclusion criteria will be enrolled and receive treatment with durvalumab + etoposide and either cisplatin or carboplatin (EP) for 4 to 6 cycles. Durvalumab will be administered at a dose of [REDACTED] every 3 weeks (Q3W) with first-line chemotherapy (EP) and will continue to be administered as monotherapy every 4 weeks (Q4W) post-chemotherapy until progressive disease (PD). Prophylactic cranial irradiation (PCI) is allowed at the investigators' discretion as per standard of care (SoC) guidance for extensive stage small-cell lung cancer (ES-SCLC). Patients will attend a safety follow up visit 90 days after last dose of durvalumab. The study flowchart is shown below in Figure 1 Overall study design.

Figure 1 Overall study design

ES-SCLC Extensive-stage small-cell lung cancer; EP etoposide + cisplatin or carboplatin; PD Progressive disease

The schedule of assessments including safety, tolerability, and efficacy using RECIST version 1.1 are detailed in the study assessment schedule in Appendix A.

Tumour assessments using computed tomography (CT)/magnetic resonance imaging (MRI) will be performed at the times specified in the schedule of assessment (Appendix A). RECIST 1.1 measurements as assessed by the Investigator will be used to derive the secondary variables of PFS, APF12, ORR, and DoR. The categorisation of objective tumour response assessment into complete response (CR), partial response (PR), stable disease (SD), progressive disease (PD) or not evaluable (NE) will be based on RECIST 1.1.

Patients will be followed for survival status every 3 months (q3m) following treatment discontinuation, until death, withdrawal of consent or the end of the study. These contacts may be conducted by phone and the survival data collected will be reported in the clinical database.

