3.2.6 DoR

Duration of response is only calculated for patients who have a best overall tumor response of CR or PR before further anti-cancer therapy after first dose.

Duration of response will be defined as the time from the date of first documented response until the date of PD or death in the absence of disease progression. The end of response should coincide with the date of PD or death from any cause used for the PFS endpoint. The time of the initial response will be defined as the date of tumor assessment for the first response of PR or CR.

If a patient does not progress following a response, then his/her duration of response will use the PFS censoring time.

DoR (months) = (Date of event or censoring – Date of first documented CR or PR before further anti-cancer therapy after first dose + 1) /30.4375, results round to 1 decimal place.

3.2.7 OS

Overall survival is defined as the time from the date of first dose of study treatment until death due to any cause. Any patient not known to have died at the time of analysis will be censored based on the last recorded date on which the patient was known to be alive. The possible last recorded date could be found from visits, AEs, concomitant medication, cancer therapy, vital signs, physical examination, lab test, study drug exposure, survival status survey and disposition of patient.

OS (months) = (Date of death or last recorded date on which the patient was known to be alive - date of first dose of study treatment + 1) /30.4375, results round to 1 decimal place.

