3.2.9 Incidence of AEs, SAEs, AESIs and AEs leading to treatment discontinuation

An AE is the development of an undesirable medical condition (other than progression of the malignancy under evaluation) or the deterioration of a pre-existing medical condition following or during exposure to a pharmaceutical product, whether or not considered causally related to the product. An undesirable medical condition can be symptoms (eg, nausea, chest pain), signs (eg, tachycardia, enlarged liver), or the abnormal results of an investigation (eg, laboratory findings). In clinical studies, an AE can include an undesirable medical condition occurring at any time, including run-in or washout periods, even if no study treatment has been administered.

The term AE is used to include both SAEs and non-serious AEs.

AEs will be collected from time of signing of informed consent throughout the treatment period and including the follow-up period up to 90 days after the last dose of durvalumab treatment.

An SAE is an AE occurring during any study phase (i.e. treatment, follow-up), that fulfils one or more of the following criteria:

- results in death

- is immediately life-threatening
- requires in-patient hospitalization or prolongation of existing hospitalization
- results in persistent or significant disability/incapacity
- is a congenital abnormality or birth defect
- is an important medical event that may jeopardize the patient or may require medical
- intervention to prevent one of the outcomes listed above

An AESI is one of scientific and medical interest specific to understanding of the Investigational Product and may require close monitoring and rapid communication by the investigator to the sponsor.

The AESIs reported in the AstraZeneca-sponsored durvalumab studies are defined as AEs that have a likely inflammatory or immune-mediated pathophysiological basis resulting from the mechanism of action of durvalumab and requiring more frequent monitoring and/or interventions such as corticosteroids, immunosuppressants, and/or endocrine therapy. Endocrine therapies include standard endocrine supplementation, as well as treatment of symptoms resulting from endocrine disorders (for example, therapies for hyperthyroidism include beta blockers [e.g., propranolol], calcium channel blockers [e.g., verapamil, diltiazem], methimazole, propylthiouracil, and sodium perchlorate, infusion-related reactions and hypersensitivity/anaphylactic reactions).

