4.1.6 Data derivation rules

The data derivation rules are describe as follows:

Table 5 Variable derivation rules

Variable (unit)	Definition	Derivation rules
Age (years)	Years from birth date to informed consent	Integer part of $((\text{date of informed consent} - \text{date of birth}) / 365.25)$
Time from first dose of study treatment to the date of disposition event (months)	Months from the date of first dose of study treatment to the start date of disposition event	$(\text{Start date of disposition event} - \text{date of first dose of study treatment} + 1) / 30.4375$, round to 2 decimal place
Time from original diagnosis to informed consent	Months from the date of original diagnosis to the date of informed consent	$(\text{Date of informed consent} - \text{date of original diagnosis}) / 30.4375$, round to 2 decimal place
BMI at each visit (kg/m ²)	Weight over squared height	Weight at each visit (kg) / height at screening (m) ² , round to 2 decimal place
Time from original diagnosis to the first	Months from the date of original diagnosis of SCLC	$(\text{Date of first dose of study treatment} - \text{date of original$

dose of study treatment (months)	to the date of first dose of study treatment	diagnosis of SCLC + 1) / 30.4375, round to 2 decimal place
Time from the latest assessment to the first dose of study treatment (months)	Months from the date of latest assessment of SCLC to the date of first dose of study treatment	(Date of first dose of study treatment – date of latest assessment of SCLC + 1) / 30.4375, round to 2 decimal place
Time to first AE (days)	Days from the date of first dose of study treatment to the date of first AE occurrence or censoring	Date of first AE or censoring – date of first dose of study treatment +1
Duration of AE (days)	Days from the AE start date to the AE stop date or date of DCO. The date used should not be imputed.	AE stop date or date of DCO – AE start date +1

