4.2.4 Primary endpoints

Adverse events, which start after first dose of study drug up to 90 days after the last dose of durvalumab treatment or the date of initiation of the first subsequent therapy, whichever occurs first, will be analysed in summary table. Other AEs recorded in the study will only be listed. This rule applies to all analysis of AE.

Frequency of AEs of CTCAE grade ≥ 3 , no. and percentage of patients with AEs of CTCAE grade ≥ 3 will be presented. These AEs will also be summarized by System Organ Class (SOC) and preferred term (PT). The exact 95% CIs around the incidence estimates will also be reported.

Time to event endpoints will be analysed using Kaplan-Meier method to estimate the median event time to the first AE of CTCAE grade 3 or higher. If a patient has no AE of CTCAE grade 3 or higher, the time to event will be censored at the date of DCO, death, 90 days after

the last dose of durvalumab treatment or the date of initiation of the first subsequent therapy, whichever occurs first. K-M curve will be presented.

Similar analyses will be conducted for imAEs.

An imAE is defined as an AESI that is associated with drug exposure and is consistent with an immune-mediated mechanism of action and where there is no clear alternate etiology. In general, imAEs will include AESIs that are managed using steroids, immunosuppressants and/or hormone replacement therapy.

The identification of imAEs will be made following the AstraZeneca imAE characterization charter.

1. The selection of preferred term,
2. Programmatic identification of those potential imAEs requiring medication such as steroids, immunosuppressants and/or hormone replacement therapy

All imAEs which are identified by the investigator (as recorded in CRF Adverse Events (AE)) will undergo a review by medical monitor. In addition, imAEs will be checked programmatically as described in the imAE charter on the clinical database to ensure the recording of imAEs are complete and unambiguous. If any discrepancies found, those will be resolved as an on-going basis and before DBL.

All above AEs will be listed.

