4.2.5.7 Incidence of AEs, SAEs, AESIs and AEs leading to treatment discontinuation

Analyses similar to the primary endpoints will be conducted for overall AEs, SAEs, AESIs and AEs leading to discontinuation of study treatment. In addition, the no. and percentage of patients with AEs will be presented by PT.

All above AEs will be listed. Detailed statement of death will be listed.

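### Time to first AE: the censoring rule in SAP 4.2.4 has no term for withdrawal of consent or loss to follow-up, so unobserved days count as AE-free time at risk

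*SAP*

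**What the plan says.** SAP section 4.2.4 analyses time to the first grade ≥3 AE by Kaplan-Meier. For a patient without such an event, "the time to event will be censored at the date of DCO, death, 90 days after" durvalumab was last given, or when a first subsequent therapy begins; the earliest applies. That is four dates: data cut-off, death, last durvalumab dose plus 90 days, and first subsequent therapy.

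The rule reaches further than one endpoint. Section 4.2.4 adds: "Similar analyses will be conducted for imAEs". Section 4.2.5.7 adds: "Analyses similar to the primary endpoints will be conducted for overall AEs, SAEs, AESIs and AEs leading to discontinuation of study treatment".

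No other section supplies a further censoring date. Table 5 in section 4.1.6 defines time to first AE as "Days from the date of first dose of study treatment to the date of first AE occurrence or censoring" without saying what censoring is. Section 4.1.7 on missing data and incomplete dates is silent on patients whose AE follow-up stops early. Section 3.2.9 sets the planned AE collection period, "including the follow-up period up to 90 days after the last dose of durvalumab treatment".

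The survival endpoints are handled differently. For OS (section 3.2.7), a patient not known to have died "will be censored based on the last recorded date on which the patient was known to be alive". For PFS (section 3.2.3), a patient without an event is censored at the latest tumour assessment.

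**The concern.** A Kaplan-Meier risk set should hold only patients in whom an event would have been seen had it happened. Last dose plus 90 days is the planned end of AE observation, not the actual one. Someone lost 10 days after the last dose is carried as event-free for a further 90 − 10 = 80 days with no data behind them.

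The error runs one way. It enlarges the denominator at each later event time, lowers the estimated cumulative AE probability and delays the median. In a study whose purpose is safety, that is the favourable direction. The 90 days after treatment are also where late imAEs would be sought.

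The other listed dates rarely help. Appendix A records survival status and subsequent therapy at the safety follow-up visit and the survival contacts. A patient who has withdrawn or been lost normally has neither, so the 90-day date applies unless data cut-off comes first. The patients with the least information are given the full follow-up.

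**Working it through.** **1. The plan's own figures.** Section 1.3 gives a precision of 5.7% at 60% incidence (grade ≥3 AEs) and 4.7% at 20% (imAEs) for 300 patients. Half the width of the Clopper-Pearson 95% interval is 5.69 points for 180/300 and 4.68 points for 60/300, so both figures reproduce. They depend only on counts and the safety set denominator, not on the censoring rule.

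**2. Direction.** The Kaplan-Meier estimate is the product of (1 − d/r) over event times, with d events among r at risk. Unobserved patients add to r and can add nothing to d. Each d/r is therefore too small, or unchanged, and the event-free curve too high.

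**3. Upper bound on unobserved time.** Only event-free patients are censored. The bound is 300 × share lost × share event-free × 90 days. The share lost is not in the SAP; 5-15% is assumed, which is 15-45 patients. The event-free share takes the section 1.3 incidences and assumes that they apply to lost patients.

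- Grade ≥3 AEs, 1 − 0.60 = 40% event-free: 15 × 0.40 × 90 = 540 days, to 45 × 0.40 × 90 = 1,620 days (1.5 to 4.4 patient-years at 365.25 days).
- imAEs, 1 − 0.20 = 80% event-free: 15 × 0.80 × 90 = 1,080 days, to 45 × 0.80 × 90 = 3,240 days (3.0 to 8.9 patient-years).

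These are upper bounds, because each lost patient is given the full 90 days and no earlier data cut-off, death or subsequent therapy.

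**4. Effect on the curve (illustrative simulation, 20,000 patients per scenario).** Assumptions not in the SAP: constant hazard giving 60% with a grade ≥3 AE by Day 260; exponential time to last durvalumab dose with mean 170 days; lost patients leave 0-30 days after the last dose; all others are observed for the full 90 days; data cut-off, death and subsequent therapy are not modelled. The hazard is −ln(0.40)/260 = 0.003524 per day, so the true median is ln(2)/0.003524 = 197 days and the true event-free probability at Day 270 is exp(−0.003524 × 270) = 0.386.

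| Share lost | Median, SAP rule | Median, censored at end of AE observation | Shift (days) | Event-free at Day 270, SAP rule | Event-free at Day 270, end of observation | Shift (points) |
|---|---|---|---|---|---|---|
| 0% | 197 | 197 | 0 | 0.385 | 0.385 | 0.0 |
| 5% | 201 | 198 | 3 | 0.395 | 0.388 | 0.7 |
| 10% | 205 | 199 | 6 | 0.397 | 0.385 | 1.2 |
| 20% | 211 | 197 | 14 | 0.417 | 0.393 | 2.4 |
| 30% | 219 | 198 | 21 | 0.431 | 0.391 | 4.0 |

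At 15% lost the median shift is about 10 days, midway between the 10% and 20% rows. Censoring at the end of observation recovers the true values to within simulation noise. The rule as written drifts away as loss rises.

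For imAEs, with 20% incidence by Day 260 and the same assumptions, the median lies far beyond the follow-up of most patients, so the curve is the better measure. At Day 270 the event-free probability is 0.794 against 0.791 at 5% lost (0.3 points), 0.799 against 0.794 at 10% (0.5) and 0.800 against 0.788 at 20% (1.2).

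If instead 80-90% of the grade ≥3 hazard falls in the first 18 weeks (also assumed), the median shift at 5-15% lost is about 1-5 days.

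**The case against.** The strongest reply is that little depends on this. Section 3.1 defines the primary endpoints as numbers and proportions of patients in the safety set, and section 4.2.4 gives them exact intervals. Neither uses the censoring rule. The study has one arm and no hypothesis test (section 4.1.3), and at plausible loss rates the shift is well inside the stated precision of 5.7 and 4.7 points. All of this stands, and it limits the weight of the point. It does not remove it. The curves and medians are planned outputs, the shift is a bias and not random error, and the rule as written produces it.

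A reader might go further and infer that a safety follow-up visit held 7 days early, on Day 83 after the last dose, opens the same gap in patients who stay in the study. The document does not support that. The ±7 days in Appendix A is a visit window. Section 3.2.9 collects AEs up to 90 days after the last dose, and section 4.2.4 counts AEs starting up to then. Censoring event-free patients at Day 83 while still counting an event on Day 88 would make censoring depend on outcome and push the AE curve up.

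A reader might also multiply all 15-45 lost patients by 90 days, giving 1,350-4,050 days. That overstates the size, because patients who already have the event are not censored. For overall AEs, where few patients are likely to be event-free, the effect is smaller still.

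Finally, section 1.2 does mention withdrawal ("until death, withdrawal of consent or the end of the study"), but that sentence governs survival follow-up. It shows that withdrawal is foreseen; it sets no end to AE observation.

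**Conclusion.** The point holds for withdrawal of consent and loss to follow-up, and only for the time-to-first-AE analyses. Section 4.2.4 states a closed list of censoring dates which, followed literally, credits up to 90 unobserved AE-free days to each event-free patient who leaves early. The bias is towards a more favourable safety profile. It affects grade ≥3 AEs, imAEs and, through section 4.2.5.7, the secondary AE endpoints. It would be wrong to conclude that the primary incidences are biased by this rule.

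The size is modest: about 3-10 days on the grade ≥3 median at 5-15% lost, and nothing with complete follow-up. This rests on an assumed loss rate, an assumed hazard shape, and lost patients having the same AE risk as the others. If patients leave because they are becoming unwell, censoring at last contact does not fully correct the curve either, but it no longer counts time that was never observed.

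**What to change.** In section 4.2.4, add to the list of which the earliest date applies: the date of withdrawal of consent or loss to follow-up, taken as the last contact at which AEs were assessed. Define this end of AE observation in the same way for all patients, with or without the event, so that events and time at risk are counted over one window. State that the change carries to imAEs and to the endpoints in section 4.2.5.7, and make the censoring entry in Table 5 refer to it.

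Do not add the date of a safety follow-up visit held within its ±7-day window as a censoring date.

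Beside the incidence tables, report how many patients lack AE follow-up to 90 days after the last durvalumab dose. The incidence proportions do not otherwise show incomplete observation.

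The cost is one clause and one row in a table. Visit and disposition data are already used elsewhere in the SAP (sections 3.2.7 and 4.2.1), so no new collection should be needed. The downside is slightly fewer patients at risk late in the curve.

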3 PRIMARY AND SECONDARY VARIABLES

3.1 Primary endpoints

Primary endpoints include incidence of grade ≥ 3 AEs and incidence of imAEs.

Incidence of grade ≥ 3 AEs: Number and proportion of patients in SS with CTCAE (version 5.0) grade ≥ 3 AEs.

Incidence of imAEs: Number and proportion of patients in SS with imAEs.

imAEs: ImAEs will be identified from AEs of special interest (AESIs) based on programmatic rules that consider interventions involving systemic steroid therapy, immunosuppressant use, and/or endocrine therapy. Endocrine therapies include standard endocrine supplementation, as

well as treatment of symptoms resulting from endocrine disorders (for example, therapies for hyperthyroidism include beta blockers [e.g., propranolol], calcium channel blockers [e.g., verapamil, diltiazem], methimazole, propylthiouracil, and sodium perchlorate).

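### Time to first AE is planned by Kaplan-Meier with death censored: the curve overstates AE probability, and the imAE median will be unreached or set by the late tail

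*SAP*

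**What the plan says.** Section 3.1 defines both primary endpoints as proportions, for example "Incidence of imAEs: Number and proportion of patients in SS with imAEs". Section 4.2.4 analyses them as counts and percentages and adds: "The exact 95% CIs around the incidence estimates will also be reported".

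Beside these, Section 4.2.4 plans a Kaplan-Meier analysis "to estimate the median event time to the first AE of CTCAE grade 3 or higher". A patient without such an AE is censored at the earliest of four dates, and death is one of them: "the time to event will be censored at the date of DCO, death, 90 days after". The 90 days run from the final durvalumab dose, and the fourth date is the start of another therapy. A graph is added: "K-M curve will be presented". No other number is named for this analysis: no probability at a fixed time and no CI for the median.

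The approach is then extended. Section 4.2.4 says "Similar analyses will be conducted for imAEs", and Section 4.2.5.7 says "Analyses similar to the primary endpoints will be conducted for overall AEs, SAEs, AESIs and AEs leading to discontinuation of study treatment". Section 4.2.8 repeats the primary and secondary endpoint analyses for PS 0, 1 and 2. It admits a level to a time-to-event analysis only if that level has 20 or more events. The SAP mentions no competing-risk method.

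**The concern.** A patient who dies without the AE can never have it. Censoring that patient treats them as still liable to the AE later, at the same rate as those who remain under observation. One minus Kaplan-Meier then estimates AE risk in a hypothetical setting without death, which is at or above the probability that patients actually face.

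Such deaths will occur. Section 3.2.9 excludes progression of the cancer under study from the AE definition, so a death from progression alone is not a fatal AE. Section 4.2.6.1 tabulates deaths due only to the disease as their own category. Any of these that fall inside the AE window without an earlier event are censored.

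The median raises a second problem. Section 1.3 assumes an imAE incidence of 20%, so most patients are expected never to have one. A median time to first imAE is then either absent or determined by very few people. At stake is how far a reader can trust the curve, and whether the time-to-imAE analysis tells them anything.

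**Working it through.** **1. The plan's own figures (Section 1.3).** With 300 patients, the Clopper-Pearson limits are 54.2% to 65.6% for 180 events (60%), a half-width of 5.69 points. For 60 events (20%) they are 15.6% to 25.0%, a half-width of 4.68 points. These match the stated 5.7% and 4.7%. They concern the crude proportions and do not depend on Kaplan-Meier.

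**2. Size of the overstatement at T = 12 months.** From the SAP: 20% imAE and 60% grade ≥3 incidence. Assumed, because the SAP gives no figure: the 12-month death risk q, constant hazards, and death as the only competing event.

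- Death hazard: d = −ln(1 − q)/T
- True cumulative incidence: CIF = a/(a + d) × (1 − exp(−(a + d)T)), with the AE hazard a solved so that CIF equals the SAP's incidence
- Reading from the planned curve: 1 − KM = 1 − exp(−aT)
- Kaplan-Meier median: ln 2 / a

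| q | d per month | a (imAE) | 1 − KM, true 20% | a (grade ≥3) | 1 − KM, true 60% |
|---|---|---|---|---|---|
| 10% | 0.0088 | 0.0197 | 21.0% | 0.0821 | 62.7% |
| 20% | 0.0186 | 0.0209 | 22.2% | 0.0891 | 65.7% |
| 30% | 0.0297 | 0.0224 | 23.6% | 0.0975 | 69.0% |
| 50% | 0.0578 | 0.0265 | 27.2% | 0.1219 | 76.8% |

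Check of the imAE figure at q = 50%: a/(a + d) = 0.314 and 1 − exp(−(a + d) × 12) = 0.636; their product is 0.20. The planned curve reads 1 − exp(−0.0265 × 12) = 27.2%.

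The excess is about 1 to 7 points for imAEs and 3 to 17 points for grade ≥3 AEs. The upper ends exceed the design half-widths of 4.7 and 5.7 points.

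**3. The median, same model.** For imAEs, ln 2 / a runs from 35.2 months (q = 10%) to 26.2 months (q = 50%). For grade ≥3 AEs it runs from 8.4 to 5.7 months.

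**4. Simulation with the other censoring reasons.** Trials of 300 patients, 200 per setting, calibrated to crude incidences of 20% and 60%. All of the following are assumptions: exponential survival with median 6 to 18 months, exponential time on durvalumab with median 6 months and independent of death, and uniform accrual over 18 months. Subsequent therapy was not modelled. Analysis is 6 months after last entry, as in Section 5.

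| | imAEs mainly early | imAE hazard constant |
|---|---|---|
| 1 − KM v cumulative incidence at 12 months, median survival 18 months | 24.3% v 21.8% | 32.4% v 26.2% |
| Same, median survival 6 months | 28.6% v 21.4% | 43.0% v 24.6% |
| Trials in which the imAE median is reached | 3.5-6.5% | 44.5-66% |
| Typical imAE median where reached | 17-21 months | 14-18 months |

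For grade ≥3 AEs the median was reached in every simulated trial, at about 2 to 5 months.

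**The case against.** **The primary results are untouched.** This is the strongest reply, and it stands. A reader might infer from the censoring rule that the primary safety estimates are biased, or that the SAP offers no usable figure for imAEs. Neither follows. The imAE endpoint is a proportion with an exact CI and a planned precision of 4.7%. Only the accompanying time-to-event part is in question.

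**No Kaplan-Meier probability is planned as a reported number.** This also stands. The overstatement affects what is read off the curve and where the median falls.

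**Mortality is not stated, and not every death is censored as a competing event.** This stands as a limit on size. A fatal AE counts as a grade ≥3 event. Deaths after the 90-day window or after subsequent therapy lie outside the period at risk.

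**The PS comparison.** A reader might infer that the Kaplan-Meier curves distort PS 2 against PS 0 and 1 because survival differs. The formulas show the opposite. 1 − exp(−aT) contains no death hazard: with a = 0.03 per month, groups with death hazards of 0.04 and 0.12 both read 30.2% at 12 months. Their cumulative incidences are 24.4% and 16.7%. Cumulative incidence is the right absolute probability, but it falls when mortality is higher, so it needs care when groups are compared. The 20-event rule also limits these analyses: at 20% incidence a PS level needs about 20/0.20 = 100 patients for an imAE curve.

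**The change will not make the curve equal the crude percentage.** Correct. Data cut-off, end of the window and subsequent therapy also separate the two. In the constant-hazard simulation the 12-month cumulative incidence was still 25-26% although about 20% of patients had an observed imAE.

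**Conclusion.** The point holds for the supportive time-to-first-event analyses in Sections 4.2.4 and 4.2.5.7. Censoring death makes one minus the planned curve overstate the probability of the AE. If 10-50% of patients die by 12 months, a true 20% imAE risk reads as about 21-27% and a true 60% grade ≥3 risk as about 63-77%. That range rests on constant hazards, death as the only competing event, and mortality that the SAP does not give. The direction of the error does not depend on those choices.

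The median is informative for grade ≥3 AEs at the assumed 60%. For imAEs at 20% it will be unreached or come from the few patients still at risk late on.

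This is a worthwhile, inexpensive improvement to a descriptive analysis, not a fault in the primary endpoints.

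**What to change.** In Section 4.2.4, and through it Section 4.2.5.7:

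- Replace the Kaplan-Meier curve for time to first AE with the Aalen-Johansen cumulative incidence, with death without the AE as the competing event. Keep data cut-off, end of the 90-day window and first subsequent therapy as censoring.
- Report the cumulative incidence with 95% CIs at fixed times, for example 3, 6 and 12 months.
- Drop the median for imAEs.
- For PS 0, 1 and 2, present the cumulative incidence together with exposure-adjusted incidence rates, and state that cumulative incidence is lower where mortality is higher. Keep the 20-event rule of Section 4.2.8.

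The cost is SAP wording and a little more programming with standard software. Death dates and exposure are already collected. The downside is that readers must be told how to interpret cumulative incidence when PS groups differ in survival.
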